### ***HIV Test Site and HIV outpatient Clinic Staff and Director Data***

In each test site, directors, physicians, nurses, and other site staff will undergo brief quantitative interviews (up to 1 hour in length) at pre-implementation and at 12 and 24 months post-implementation. These interviews will be administered with Qualtrics to assess acceptability of the intervention and site context including organizational readiness to change, implementation leadership, and implementation climate (Table 1). Site staff will also undergo a 3-question survey at 6-10 months post endline, as described in Section 5.4. Qualitative in-depth interviews will be conducted after 24 months post-implementation and 6-10 months post-endline, as described in Section 5.4, at HIV test sites and HIV outpatient clinics.

#### ***5.5.1 Visit Procedures for PWID Participants: Post-implementation (Appendices I-III)***

If the PWID accepts the SNaP intervention and is eligible and willing to participate in the implementation trial, the following procedures will occur as part of study enrollment:

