### 3.2. Study Population

#### **3.2.1 PWID Participants:**

PWID at the test sites will be enrolled with two levels of engagement for assessment of effectiveness outcomes (Aim 1):

- 1) For ART and MAT uptake outcomes, eligible participants will: test HIV-positive using the standard confirmatory HIV test in Vietnam; be 18 years or older; report a history of injection drug use in the past 6 months; and live in the HIV treatment catchment area.

*Only PWID, not all HIV-infected persons, will be offered SNaP at the selected HIV test sites.* We conservatively estimate ~6200 eligible PWID over 21 months, after accounting for deaths. Most PWID will provide consent only for medical record assessment and will not be re-contacted.

- 2) For viral suppression, a subset of enrolled HIV-infected PWID will be selected and asked to additionally consent to re-contact. This subset (n=1500, target n=1200 with 20% loss to follow-up) will provide contact information and undergo an interview at baseline. This group will be re-contacted (see Sections 3.5.1 and 5.5 for retention strategy) for interview and assessment of viral suppression at 12 and 24 months after site implementation.

A sample of PWID (Sections 5.4, 5.5.1) will also be selected to participate in qualitative interviews after 24 months post-implementation, to assess high and low site performance characteristics (Aim 3).

Women are a minority of PWID and HIV-infected persons in Vietnam. We will engage women in the study in a proportion representative of the HIV-infected PWID population.

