## **3.3. Inclusion Criteria**

### *PWID participants:*

- 1) HIV infection:
  - Newly diagnosed HIV infection, based on confirmatory test at the test site, and not currently on ART at the time of the study; **or**
  - If previously diagnosed with HIV infection, then not currently on ART at the time of study enrollment (self-reported)
- 2) Age 18 years or older
- 3) Injection drug use within the past 6 months (self-reported at time of screening)
- 4) Willingness to provide informed consent

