#### **3.5.1 Persons who inject drugs (PWID)**

All persons meeting the eligibility criteria presenting to 42 HIV test sites in Vietnam will be approached for inclusion in the study. Recruitment will immediately follow routine post-test counseling procedures. Eligible persons will be informed of the study and consent will be requested to access their medical records at local HIV and methadone clinics. In addition, consent will be requested for audio-recording of psychosocial counseling sessions. Retention for the primary study participants is not required, as the only follow-up is through medical record review.

In a subset of the primary study participants (n=1500), we will also obtain consent for re-contact at a later date. These participants will be contacted by telephone and undergo a brief interview. Retention will be facilitated by quarterly contact by telephone to ensure that the number has not changed. If we are unable to reach a participant, we will contact a family member or friend, using a contact number provided during the original consent process.

The expected overall number of PWID is ~335 per month for 21 months or 7035. After accounting for approximately 12% mortality, as seen in a previous study, the expected number of PWID for outcome measurement is ~6200.

We will enroll a subsample cohort of 1500 PWID to obtain a sample of 1200 PWID for detailed assessments, including questionnaires and viral load determination. We recruit all eligible PWID into this subsample cohort, until we reach the 1500 sample size. **The 1500 allows for a 20% loss to follow-up (evaluable n=1200).**

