## 4. STUDY INTERVENTION AND IMPLEMENTATION PACKAGES

### 4.1. Evidence-based Intervention: Systems Navigation and Psychosocial Counseling (SNaP)

PWID with confirmed HIV infection at the test site will receive the SNaP integrated intervention that includes: 1) systems navigation to facilitate engagement and retention in HIV care and MAT (currently methadone in Vietnam), and to negotiate required laboratory tests (e.g. CD4 counts) or transportation; and 2) psychosocial counseling using motivational interviewing, problem solving, skills building, and goal setting to facilitate ART and MAT initiation and adherence.

As an implementation study, navigators/counselors will not be compensated by the study.

Systems navigators will initially meet participants twice, in-person or by telephone, within 8 weeks of enrollment. Subsequent sessions, based on participants' needs, will be conducted in-person, by telephone, or SMS text.

Psychosocial counselors will provide participants with a minimum of one counseling session within 4 weeks of enrollment. The session will focus primarily on ART initiation, ART adherence and MAT. To determine the need for additional sessions, the counselor will use a standardized inventory to assess the participants' need for counseling on risk reduction, drug treatment entry and retention, HIV medical care, ART and MAT adherence, depression, alcohol dependence, and social support. Counseling session content will be incorporated in a manual, similar to that used in HPTN 074, which will be used by the counselors to ensure coverage of key topics and specific psychosocial counseling techniques. Participants will be offered the opportunity for additional booster sessions, if needed, at ~1 and 3 months after enrollment. Participants who have not initiated ART, have low levels of adherence to ART, or have not begun MAT will be able to receive additional counseling sessions through self-referral or referral by the systems navigators.

We will train existing HIV test site staff, selected by test site directors, to become systems navigators and psychosocial counselors for SNaP.

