#### **5.4.1 High and Low Performing and Sustaining Sites Data Collection:**

In-depth interviews - PWID at high and low performing sites: We will conduct six semi-structured in-depth interviews (IDIs) with PWID in each of three sites of the following four site performance types (12 test sites; 72 interviews): 1) SA low performers; 2) SA high performers; 3) TA low performers; and 4) TA high performers. Three PWID will have participated in SNaP and three PWID will have declined SNaP. We will ask participants about barriers and facilitators to uptake of ART and MAT and ART adherence, attitudes and experiences in the HIV test site, with test site staff, and if appropriate, with navigators and counselors.

In-depth interviews - navigators and counselors, clinic staff, and clinic directors: In these same 12 test sites, we will conduct semi-structured IDIs with navigators/counselors (n=12-24), site staff (n=12), site directors (n=12) and HIV providers (n=12) to inform the context and processes that may underlie SNaP success and failures (total n=48-60, depending on the number of navigators and counselors at each site). Topics will include PWID-related stigma; attitudes toward and experience with SNaP, SA, and TA

implementation packages; competing site priorities; perceptions of rewards and leadership support around SNaP; perceptions of effectiveness of SNaP, SA and TA; availability of technical assistance; beliefs around sustainability of SNaP at their test site; collaboration between HIV test sites and HIV outpatient clinics.

Quantitative characterization of high and low performing clinics: We will use the implementation test site context scales for readiness to change, implementation leadership, and implementation climate to characterize each clinic before and after implementation of SNaP. We will also characterize the test sites in terms of overall size (number of HIV tests performed), PWID size (number of HIV tests performed who are PWID), PWID proportion (number of PWID over total tests performed), staff information and current support from NGOs Clinic and PWID characteristics will be assessed before and after implementation.

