### **PWID Data**

**PWID enrollment:** All PWID who are confirmed HIV-infected will be given a brief consent form during post-test counseling. This consent will address permission to: 1) extract ART uptake from medical records at local ART clinics and 2) extract MAT uptake from medical records at MAT clinics. Note that consent for SNaP will not be explicitly requested, as it will be considered a routine clinical activity at that site upon trial initiation.

**ART and MAT uptake data:** To initiate ART, all persons in Vietnam must present a confirmation of diagnosis to the ART clinic. Using participants' study masked ID (MID), we will then review the medical record at ART clinics to confirm ART initiation. A similar process will be used for MAT uptake data. **These data will be extracted semi-annually.**

**Viral suppression and interview data:** During months 0-6 and 12-18 after implementation in each test site, a random sample of PWID will be identified for participation in the subsample cohort. These PWID will have an additional consent to allow re-contact and to obtain locator information, including a family member. A few days after diagnosis, the PWID subsample cohort will undergo a brief demographic, behavioral, mental health, and costing questionnaire, administered through the phone by a test site staff member trained and compensated to collect these data.

To enhance retention, the subsample cohort of 1500 PWID will be re-contacted every 3-4 months to maintain contact. If contact with the PWID cannot be established, the family member will be contacted in an attempt to update the locator information. Trained study staff (including training in confidentiality) will attempt to contact family members by phone. If after several attempts the family members are not reached by phone, our trained study staff will attempt to visit the home. (See also **Section 9.6.1.**)

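### Section 5.5.1 makes accepting SNaP a condition of enrolment, contrary to the eligibility, recruitment and consent sections, and so leaves the planned interviews with decliners outside the enrolled pool

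*Combined protocol and SAP*

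**What the plan says.** **Entry to the study**
- Section 5.5.1 introduces the enrolment procedures, for PWID both inside and outside the subsample cohort, with "If the PWID accepts the SNaP intervention and is eligible and willing to participate in the implementation trial".
- Section 3.3 lists HIV infection without current ART, age, recent injection and "Willingness to provide informed consent". Neither it nor the exclusions in 3.4 (residence, current ART, plans to move) mentions acceptance of SNaP.
- Section 3.5.1: "All persons meeting the eligibility criteria presenting to 42 HIV test sites in Vietnam will be approached for inclusion in the study".
- Section 5.5, PWID Data: "All PWID who are confirmed HIV-infected will be given a brief consent form during post-test counseling". It adds: "Note that consent for SNaP will not be explicitly requested, as it will be considered a routine clinical activity".
- Section 5.5.1.1 has SNaP offered whether or not the person joins the trial.

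**What depends on entry**
- Section 4.1: "Systems navigators will initially meet participants twice, in-person or by telephone, within 8 weeks of enrollment". The one required counselling session is due within 4 weeks of enrolment.
- Section 7.2.1 scores fidelity from the percentage of expected sessions completed, weighted by quality. It does not say for which persons sessions are expected.
- Section 5.4.1, on six PWID interviews at each of 12 sites: "Three PWID will have participated in SNaP and three PWID will have declined SNaP".
- Section 3.2.1: "Most PWID will provide consent only for medical record assessment and will not be re-contacted". The same section later says a sample will be selected for qualitative interviews.
- Section 8.2.1 promises intent-to-treat comparisons between arms.

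**The concern.** A site could enrol every eligible PWID who consents, or only those who also accept SNaP, and claim compliance either way.

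Under the 5.5.1 rule, acceptance decides who is in the study. Acceptance follows site randomisation, and implementation support is exactly what differs between the tailored (TA) and standard (SA) arms. The enrolled groups could then differ by arm for a reason the arms themselves produce. Section 8.3 plans to count people who decline the study, but not people who decline SNaP. Nor could a later change to the ART-uptake denominator bring back people who were never enrolled.

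The same rule undercuts Aim 3. Half of the PWID interviews are meant for people who declined SNaP, yet the PWID interview procedures appear only under 5.5.1.1, 5.5.1.2 and Appendices I and II, all of which describe enrolled participants.

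**Working it through.** **1. The entry rules side by side**

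| Section | Eligible | Consents to study | Accepts SNaP |
|---|---|---|---|
| 3.3 and 3.4 | required | required | not mentioned |
| 3.5.1 | required | requested | not mentioned |
| 5.5, PWID Data | confirmed HIV infection | requested | consent for SNaP not requested |
| 5.5.1 | required | required | required |

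Only 5.5.1 has the extra condition, and 5.5 provides no documented acceptance step at that visit on which to apply it.

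**2. Interviews affected**

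Section 5.4.1: 12 sites × 6 = 72 PWID interviews, of which 12 × 3 = 36 are with decliners. Under 5.5.1 none of the 36 is in the enrolled pool. Under 5.5, decliners may be in the subsample cohort, which gives locator details and consents to re-contact. The cohort averages 1500 / 42 = 35.7 per site, or 1200 / 42 = 28.6 after the plan's 20% loss to follow-up. If 10% decline, that is 35.7 × 0.10 = 3.6 decliners per average site before loss and 28.6 × 0.10 = 2.9 after it, against 3 needed. If 20% decline, it is 7.1 and 5.7. These refusal rates are assumptions. Section 8.1.2 expects site sizes from 7 to 764, so small sites would have fewer. PWID outside the cohort have no locator entry in Appendix I, although the same table schedules interviews for them.

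**3. The plan's fidelity figures (Section 8.1.1)**

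- TA: 200 × 0.80 × 0.85 = 136.
- SA: 200 × 0.75 × 0.67 = 100.5, or 200 × 0.75 × 0.74 = 111.
- Two-sample t-test, 21 sites per arm, two-sided 0.05, noncentrality = difference / (SD × √(2/21)):
  - difference 35.5, SD 40: 2.88, power 80.1%;
  - difference 25, SD 28: 2.89, power 80.6%.

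The stated 80% is reproduced in both cases.

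**4. Fidelity if decliners count (illustration only)**

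Assume that the plan's scores apply to acceptors, that a share d declines equally in both arms, and that decliners complete no session. The score over all enrolled is then the acceptor score × (1 − d).

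| d | TA, from 136 | SA, from 111 | Difference |
|---|---|---|---|
| 0% | 136 | 111 | 25 |
| 10% | 122.4 | 99.9 | 22.5 |
| 20% | 108.8 | 88.8 | 20 |
| 30% | 95.2 | 77.7 | 17.5 |

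If every site's score scales by the same factor, so does the SD. At d = 20%, 20 / (0.8 × 28) = 0.893 = 25 / 28, and power is unchanged. If the SD stayed at 28, power at d = 20% would be 62%. The documents do not settle which applies.

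With unequal refusal, say 10% in TA and 20% in SA, and 136 among acceptors in both arms, the arm difference is 136 × 0.90 − 136 × 0.80 = 13.6 over all enrolled and 0 among acceptors.

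**5. The success threshold (Sections 5.4 and 7.5)**

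The plan's best-case score is 153. Over all enrolled, it falls below the threshold of 136 once acceptance is under 136 / 153 = 89%.

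**The case against.** The strongest reply is that the 5.5.1 clause is loose drafting. The formal criteria have no acceptance condition and consent for SNaP is not requested, so there may be no gate for a site to apply. That limits the seriousness, but the clause still heads the operative list of enrolment procedures and contradicts four other sections.

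It can also be said that losses at the offer are already measured. Penetration (7.2.2) is a secondary outcome, and the testing logs in 5.5 supply a denominator of diagnosed PWID that is independent of enrolment. This stands: fidelity and penetration are separate constructs in the plan, and whether refusals belong in fidelity is a matter of judgement.

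Three stronger readings are tempting, and the documents do not support them.

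- A reader might infer that the fidelity score necessarily changes with the enrolment rule. The 4.1 windows start at enrolment, which suggests a link. But completion is read from logs that Section 5.6 keeps for PWID already in a navigator's or counsellor's care, and a denominator of people taking part in SNaP fits that at least as well.
- A reader might set the 27.2-point fall at 20% refusal against the 25-point difference the plan can detect. These are unlike quantities: a fall common to both arms is not an arm difference.
- A reader might infer that decliners can never be reached, or would be contacted without permission. Section 3.2.1 says most, not all, PWID will not be re-contacted; interviews have their own consent step; and under 5.5 cohort members agree to re-contact. The consent forms are not in the document reviewed, so what others agree to cannot be judged.

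**Conclusion.** The contradiction is certain, since it is in the text. Followed as written, 5.5.1 selects participants after site randomisation on an event the arms may influence, which does not fit the intent-to-treat comparison, and it puts all 36 decliner interviews, half of the 72, outside the enrolled pool. The size of any resulting bias cannot be stated, because no refusal rate is given by arm or overall.

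The effect on fidelity is conditional on two things the plan leaves open: whether sessions are expected of enrolled decliners, and how many decline. The 122.4 and 108.8 are illustrations under assumed refusal of 10% and 20%, and no change of sample size follows from them. What is firm is that a primary outcome has an undefined denominator.

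This should be fixed. It does not by itself invalidate the primary analysis.

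**What to change.** - **5.5.1:** delete the acceptance condition from the opening sentence, so that enrolment is eligibility plus consent, as in 3.3, 3.5.1 and 5.5. Record acceptance or refusal of SNaP for each enrolled PWID.
- **7.2.1:** state for whom sessions are expected. Name one denominator as primary and report the score both for all enrolled PWID and for SNaP acceptors.
- **5.4 and 7.5:** tie the 136 success threshold to whichever denominator is primary.
- **5.4.1 and the appendices:** define a decliner, and draw decliners from enrolled PWID with permission for re-contact: the subsample cohort, or others through an optional contact item on the enrolment consent.
- If enrolment has started by the time of the change, report which entry rule sites applied.

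The cost is a few sentences and one optional consent item. The real downside is that an all-enrolled score would be lower and closer to penetration, so the threshold and the assumptions in 8.1.1 would need checking if that score were made primary.

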##### **5.5.1.1 PWID Not in Subsample Cohort (n= approx. 5000)**

PWID who present to one of the 42 selected HIV test sites at any time point post-implementation of SNaP at that site will be offered the SNaP intervention, regardless of PWID participation in the implementation trial (see also **Appendix I**):

###### ***Enrollment Procedures:***

Administrative, Behavioral, and Regulatory Procedures

- Informed consent to participate in the implementation trial
  - Consent will be obtained during post-test counseling at the site
- Bar code sticker placed on PWID's HIV confirmation test result card

Laboratory Evaluations

- No laboratory evaluations

###### ***12-Month and 24-Month Follow-up Procedures:***

Administrative, Behavioral, and Regulatory Procedures

- None
  - No direct contact with participant for follow-up procedures
  - Only the participant's ID will be used at ART and/or MMT clinic if the participant presents to either of those clinics after enrollment

Laboratory Evaluations

- None

***Post-24-Month Assessment Qualitative Interview Procedures [among randomly selected PWID at 12 selected sites] (see Section 5.4.1):***

Administrative, Behavioral, and Regulatory Procedures

- Informed consent to participate in qualitative in-depth interview
- Qualitative in-depth interview

**5.5.1.2 PWID Subsample Cohort (n=1500)**

The subset of 1500 enrolled PWID will be selected to participate in a PWID subsample cohort that will provide locator and contact information, and be re-contacted to participate in study follow-up procedures (see also **Appendix II**). We will recruit all eligible PWID into this subsample cohort, until we reach the 1500 sample size. A subset of the PWID subsample cohort will be selected to complete additional costing questions at baseline and a single follow-up visit of 12 or 18 or 24 months, depending on PWID enrollment time.

***Enrollment Procedures:***

Administrative, Behavioral, and Regulatory Procedures

- Informed consent to participate in the implementation trial
  - Consent will be obtained during post-test counseling at the site
- Additional informed consent
  - To allow for re-contact and follow-up study procedures
- Provide locator information
- Quantitative questionnaire (through phone interview)

Laboratory Evaluations

- No laboratory evaluations at enrollment

***12-Month Follow-up Procedures:***

Administrative, Behavioral, and Regulatory Procedures

- Quantitative questionnaire (through phone interview)

Laboratory Evaluations

- Dried blood spot specimen collection

***18-Month Follow-up Procedures:***

Administrative, Behavioral, and Regulatory Procedures

- Quantitative questionnaire (through phone interview)

Laboratory Evaluations

- Dried blood spot specimen collection

***24-Month Follow-up Procedures:***

Administrative, Behavioral, and Regulatory Procedures

- Quantitative questionnaire (through phone interview)

Laboratory Evaluations

- Dried blood spot specimen collection

**Post-24-Month Assessment Qualitative Interview Procedures [among randomly selected PWID at 12 selected sites] (see Section 5.4.1):**

Administrative, Behavioral, and Regulatory Procedures

- Informed consent to participate in qualitative in-depth interview
- Qualitative in-depth interview

**5.5.2 Visit Procedures for Test Site Directors and Site Staff Participants**

See also **Appendix III**.

**Pre-Implementation Baseline Assessment Procedures:**

Administrative, Behavioral, and Regulatory Procedures

- Informed consent to participate in the implementation trial
- Quantitative questionnaire via Qualtrics
  - To assess HIV test site characteristics (site demographics and site context)

